## **7 ADVERSE EVENT REPORTING**

### **7.1 Adverse Events**

Adverse events include any new or worsening of a medical condition. Adverse events are not limited to those related to study drug.

#### **7.1.1 Serious Adverse Events**

A serious adverse event may include those that result in death, life-threatening events, inpatient hospitalization or prolonged hospitalization, disability/incapacity, congenital anomaly/birth defect, important medical event, suspected transmission of an infectious agent through the study drug, and the case of the current study pregnancy.

#### **7.1.2 Non-serious Adverse Events**

A non-serious adverse event includes adverse events that are not considered serious adverse events.

#### **7.1.3 Assignment of Adverse Event Intensity and Relationship to Dupilumab**

Adverse events are graded as mild (grade 1) for those that are noticeable but easily tolerated; moderate (grade 2) for those that cause enough discomfort that there is some interference with usual activity; severe (grade 3) for those that lead to an inability to perform usual activities; very severe (grade 4) for those that are debilitating causing significant incapacitation even with symptomatic treatment. An adverse event may be related (reasonable causal relationship between dupilumab administration and the event) or not related (no reasonable causal relationship between dupilumab administration and the event). A reasonable causal relationship denotes that there are facts or other arguments suggesting a positive causal relationship.

## **7.2 Collection and Reporting**

When documenting adverse events the diagnosis is preferable to symptoms. Information that should be collected for adverse events include: onset, duration, intensity, and seriousness of the event, relationship between the event and dupilumab, resulting action taken, and any required treatments (should be documented in the medical record).

### **7.2.1 Serious Adverse Event Collecting and Reporting**

Serious adverse event collection should begin at the time that informed consent is obtained. All serious adverse events must be collected and reported, including those that occur within 30 days after the final dupilumab dose. If a serious adverse event occurs after this period, but is related to dupilumab or procedures performed in the study these should also be reported. If there is uncertainty whether an event is a serious one, a serious adverse event report should be completed. All serious adverse events, whether related or not related to dupilumab, must be reported to Regeneron within 24 hours.

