We will recruit 30 patients with allergic contact dermatitis 18 years of age and older up to 6 months after patch testing with a documented IGA of at least 3 at baseline and screening visits, and at least one 2+ (strong) or 3+ (extreme) reaction on patch testing to participate in this open-label pilot study. If more than one 2+ (strong) or 3+ (extreme) reactions are present, up to two may be selected for evaluation in the study. Priority will be given to nickel, fragrance mix I or II, and rubber as these allergens have been studied previously with respect to their preferential T helper cell skewing. At the initial screening visit, demographic information will be obtained, inclusion and exclusion criteria as detailed in Section 4.2 will be reviewed, and informed consent obtained for those deemed eligible for enrollment. A single subcutaneous dose of 600 mg will be self-administered at week 0 +72-120 hours and 300 mg every 2 weeks thereafter for a total 10 weeks of therapy. Subjects will be evaluated for improvement in primary and secondary endpoints using clinical examination and questionnaires during initial and follow-up visits at Week 0, Week 6, and Week 12 as per Time and Events Schedule. Patch test site reactions will also be evaluated 72 hours after the Week 0 and Week 12 visits. Skin biopsies will be taken at these two time points from both the patch test site reaction and from normal skin taken from a non-dermatitic area on the contralateral side of the body. For the Week 12 patch placement, a site contralateral to the Week 0 patch placement site will be chosen. If an area of persistent dermatitis other than the patch test site(s) is also present at week 12+72-120 hours an additional biopsy will be taken unless in an anatomic location not amenable to biopsy (face, hands, elbows, knees, genitals, feet). Serum samples will be obtained at four time-points including Week 0 (prior to patch placement), Week 0 +72-120 hours, Week 12 (prior to patch placement), and Week 12 +72-120 hours. If subjects do not mount a 2+ (strong) or 3+ extreme reaction to the tested allergens at the Week 0 +72-120 hour visit they will be discontinued from the study and will not receive dupilumab. These patients will be considered screen fails. Week 10 +72-120 hours will conclude the end of the treatment portion of the study. Week 12 +72-120 hours will conclude the subjects' participation in the study.

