### **4.2.2 Exclusion Criteria**

Any of the following exclusion criteria would prohibit patient participation in the study:

1. Prior dupilumab use
2. Treatment with a systemic immune-regulating medication within 3 months of the baseline visit or the patient's prior patch testing, whichever is longer. Examples of these medications include azathioprine, methotrexate, mycophenolate mofetil, Janus kinase inhibitors, and phototherapy (including tanning booths). Cyclosporine or prednisone may not have been used within 1 month of the baseline visit.
3. Treatment with other biologic agents, such as TNF inhibitors, anti-IL 17 agents, anti-IL 12/23 agents, or anti-IL 23 agents, within 4 months of baseline visit or the patient's prior patch testing, whichever is longer.

4. Use of rituximab within at 6 months (or until lymphocyte counts have normalized if longer than 6 months) of the baseline visit or the patient's prior patch testing, whichever is longer.
5. Treatment with topical corticosteroids, topical phosphodiesterase inhibitors or topical calcineurin inhibitors within 1 week before the baseline visit
6. Other active conditions, such as psoriasis, that may confound clinical evaluations of dermatitis and patient-reported symptoms.
7. Increased risk of infection or reactivated infection, including history of human immunodeficiency virus, hepatitis B, hepatitis C, endoparasitic infections, receipt of a live attenuated vaccine within 3 months of the baseline visit, chronic or acute infection requiring treatment within 4 weeks of the baseline visit, immunosuppressed status (ie recurrent or resistant opportunistic infections)
8. Malignancy within 5 years of the screening visit excluding local cutaneous squamous cell carcinoma, basal cell carcinoma or cervical carcinoma in situ that has been fully treated.
9. Women who are or plan to become pregnant or breastfeed during study participation or are unable or not willing to use birth control during the study and for 4 months after the last dose of dupilumab. Options for birth control include abstinence, double barrier (ie male condom and female diaphragm), vasectomy, intrauterine device, and hormonal contraception. Females who have not had menses within 1 year of the baseline, bilateral tubal ligation, hysterectomy, and/or bilateral oophorectomy visit do not require additional methods contraception during study participation.

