## **5.3 Timing of Dose for Each Subject**

Two doses of dupilumab, 300 mg/2 mL, will be administered subcutaneously using the prefilled syringe at week 0 +72-120 hours and one dose dupilumab, 300 mg/2 mL, will be administered subcutaneously every two weeks thereafter continuing until week 10 +72-120 hours.

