## **7.3 Pregnancy**

Pregnancy should be considered a serious adverse event in the case when a subject is found to be pregnant while taking dupilumab.

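### Serious adverse events must be collected for 30 days after the last dose, but participation ends about two weeks after it, and no scheduled contact covers the rest of the window

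*Combined protocol and SAP*

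**What the plan says.** Section 7.2.1 sets the duty: "All serious adverse events must be collected and reported, including those that occur within 30 days after the final dupilumab dose". It covers related and unrelated events. Section 7.2.1 also asks for later events to be reported if they are related to the drug or to study procedures.

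The calendar is set elsewhere. Section 5.3 has dosing "every two weeks thereafter continuing until week 10 +72-120 hours". Section 4.1 agrees: "Week 10 +72-120 hours will conclude the end of the treatment portion of the study". Section 4.1, like the synopsis, then closes follow-up: "Week 12 +72-120 hours will conclude the subjects' participation in the study".

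In the Time and Events Schedule (Section 6.1) the last planned visit is Visit 6, Day 87. The only other column is for early termination or unscheduled visits. Section 9.4.2 gives one means of eliciting adverse events, which is to ask at follow-up visits. The synopsis also has a follow-up entry of three months after FV. It does not define FV, and no visit or procedure in the schedule corresponds to the entry.

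On pregnancy, Section 7.1.1 lists it among the serious adverse events for this study without a time limit. Section 7.3 applies that status "in the case when a subject is found to be pregnant while taking dupilumab".

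**The concern.** The collection window runs past the end of participation. For a subject who takes the full course, a new serious event in the second half of the 30 days becomes known only if the subject reports it or happens to be seen. A report of no late serious events would then be hard to tell apart from no one having asked.

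The trial has one open-label arm and no data monitoring committee (Section 8), so its safety information depends on complete collection. The second round of skin biopsies is also taken at Visit 6. Section 7.2.1 covers events related to study procedures, yet no contact is scheduled after those biopsies.

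**Working it through.** **Inputs.** Collection window: 30 days (Section 7.2.1). First dose: Week 0 +72-120 hours, shown as Day 4. Last visit: Week 12 +72-120 hours, shown as Day 87. Visit window: ±3 days (Section 6.1). Dosing interval: 14 days (Section 5.3).

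**The plan's own dose count.** The synopsis gives 7 doses over 10 weeks. Two syringes at the first occasion plus one each at Weeks 2, 4, 6, 8 and 10 make 2 + 5 = 7. This reproduces the figure and places the last dose at Week 10 +72-120 hours.

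**Formula.** Days observed = last visit − last dose. Share not covered = (30 − days observed) / 30.

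**Nominal timing.**
- By week labels: 12 weeks − 10 weeks = 14 days observed; 30 − 14 = 16 not covered; 16/30 = 53%.
- By schedule day numbers: last dose Day 4 + 70 = 74; 87 − 74 = 13 days observed; 30 − 13 = 17 not covered; 17/30 = 57%. The window closes at Day 74 + 30 = 104.

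The two differ by a day because the schedule labels Week 0 as Day 1 but Week 12 as Day 84, where counting from Day 1 would give Day 85.

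**Sensitivity to timing.** The plan states no window for the self-administered Week 10 dose. Applying ±3 days to it is an assumption.

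| Case | Days observed | Days not covered | Share |
|---|---|---|---|
| 72-120 h range at both ends | 12 to 16 | 18 to 14 | 60% to 47% |
| ±3 days on Visit 6 only (day numbers) | 10 to 16 | 20 to 14 | 67% to 47% |
| ±3 days on dose and visit, opposite directions (day numbers) | 7 to 19 | 23 to 11 | 77% to 37% |
| Same, from the 14-day base | 8 to 20 | 22 to 10 | 73% to 33% |

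A gap remains in every case.

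**The synopsis follow-up entry.** Taking three months as 91 days:
- If FV is the Week 0 visit (Day 1): 1 + 91 = Day 92, which is 92 − 74 = 18 days after the last dose. This leaves 12 of 30 days (40%) uncovered, and no contact is scheduled on that day in any case.
- If FV is the screening visit, at the earliest Day −34: −34 + 91 = Day 57, before the last dose.
- If FV is the final visit: 87 + 91 = Day 178, past the window. That would conflict with the stated end of participation, and again no procedure is attached.

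**Who is affected.** A subject still attending on Day 87 is fully covered only if the last dose was on or before Day 87 − 30 = 57. Planned dose days are 4, 18, 32, 46, 60 and 74, so that means stopping at the Week 6 dose (Day 46) or earlier. An early-termination visit soon after the last dose leaves a larger gap than the nominal one.

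**Pregnancy.** The schedule has a pregnancy test at the Week 12 visit (Day 84), which is 84 − 74 = 10 days after the last dose. Section 7.1.1 would class a positive result as a serious adverse event. Whether Section 7.3 does depends on whether a subject 10 days past the final injection is still taking the drug, which the plan does not say.

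**The case against.** The strongest reply is that Section 7.2.1 imposes a duty to collect and report, not a duty to hold a visit. It expects some reports outside visits, since it asks for related events after 30 days. The schedule provides for unscheduled visits that include adverse events, Section 7.2.2 has known non-serious events followed until they resolve or stabilise, and subjects come from the site's own clinic. This stands to the extent that the window is not unobservable and subjects are not out of reach. It does not supply a planned step that looks for new serious events, because following known events does not find new ones.

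It is also fair that the trial is a small pilot (at most 30 subjects) with no safety endpoint among its objectives, and that the uncovered share falls below half at the favourable end of the windows.

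Three stronger readings are tempting and are not supported:
- A reader might infer that there is no contact at all after Visit 6. The documents show only that none is scheduled.
- A reader might cite the median of 10 weeks to undetectable drug in Section 1.3.2 to enlarge the problem. That figure follows a steady-state dose, and the same section puts steady state at Week 16, whereas dosing here stops at Week 10. It also has no bearing on whether a 30-day window is met.
- A reader might set the contraception requirement in exclusion 9 ("during the study and for 4 months after the last dose of dupilumab") against Section 7.3 as a contradiction. One is an eligibility condition and the other classifies an event, so they can coexist. The real inconsistency on pregnancy is between Sections 7.1.1 and 7.3.

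**Conclusion.** The point holds for subjects who take the planned Week 10 dose. The required 30-day collection period and the stated end of participation are not reconciled, and 16 to 17 of the 30 days (53% to 57%) have no scheduled ascertainment of new serious adverse events. Across the dose and visit windows the share is roughly 33% to 77%. The result assumes 14-day dosing intervals from Day 4 and, for the widest range, that the ±3-day window also applies to the last dose.

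The synopsis follow-up entry does not close the gap. Beside the first-patient and last-patient first-visit dates, FV most naturally means first visit, which ends before Day 104, and nothing is scheduled under any reading.

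The consequence is possible under-counting of late serious events, with no effect on the primary or other efficacy endpoints. It is worth correcting because the window is mandatory and the remedy is cheap. The pregnancy wording is a separate, smaller inconsistency.

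**What to change.** Add one remote contact, by phone or Zoom, 30 days after each subject's last dose, to ask about adverse events. Tying it to the actual last dose also covers subjects who stop early. Enter it in the Time and Events Schedule, and align with it the end-of-participation sentences in the synopsis and Section 4.1 and the synopsis follow-up entry, defining FV there.

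Separately, reconcile Sections 7.1.1 and 7.3 so that it is clear how a positive Week 12 pregnancy test is classified. Which rule applies is for the sponsor and the investigator to decide.

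The cost is one short call per subject by existing staff and a small amendment. Exclusion 12 already requires subjects to be able to use Zoom. No dose, procedure or eligibility criterion changes.

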### **7.2.2 Non-Serious Adverse Events (NSAEs) Collecting and Reporting**

Non-serious adverse event collection should begin at the time that dupilumab is first administered. These events should be monitored until they resolve or become stable. Non-serious adverse events may also become serious adverse events.

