### **4.2.1 Inclusion Criteria**

The following inclusion criteria are required for patient participation in the study:

1. At least 18 years of age
2. At least one contact allergen with a 2+ (strong) or 3+ (extreme reaction) confirmed by patch testing within 18 months of the baseline visit that can be duplicated at the initiation of the study (placement at Week 0 and patch test reaction read at Week 0 +72-120 hours).
3. Allergic contact dermatitis diagnosed clinically by the principle investigators who have expertise in allergic contact dermatitis
4. Investigator's global assessment score of at least 3 (range 0-4) at the screening and baseline visits
5. Documented recent history (within 18 months of patch testing) of inadequate response to treatment with topical medications and allergen avoidance
6. Able and willing to provide informed consent, participate in study visits, and undergo visit procedures.

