# **6 STUDY ASSESSMENTS AND PROCEDURES**

## **6.1 Time and Events Schedule**

Time and events schedule is detailed in the table below:

Visit Number	1 Screening	2 Week 0	3 Week 0 +72-120 Hours	4 Week 6	5 12 Weeks	6 12 Weeks +72-120 hours	7 Early Termination /Unscheduled Visit
---------------------	------------------------	-------------------------	---	-------------------------	---------------------------	---	---

Day (+/- 3 days)	-34 to 0	1	4	42	84	87	N/A
Informed eConsent	X						
Inclusion/Exclusion Criteria	X						
Medical History	X						
Prior/Concurrent Medications	X						X
Safety Assessments							
Adverse Events		X	X	X	X	X	X
Clinical Efficacy Assessments							
Patch Test Site Reaction			X			X	
IGA	X	X		X	X		X
EASI		X		X	X		X
BSA		X		X	X		X
Patient-Reported Outcomes							
DLQI		X		X	X		X
NRS Itch		X		X			X
SLEEPYQ		X		X	X		X
Distribute Diaries (Allergen Avoidance and Dupilumab Dosing)		X					
Collect Diaries (Allergen Avoidance and Dupilumab Dosing)						X	X
Laboratory Assessments							
Pregnancy Test	X	X		X	X		X
Biomarker Skin Sample			X			X*	
Biomarker Serum Sample		X	X		X	X	
Medication Dosing							
In-Office Dosing			X				
Dispense Study Medication			X	X			
Patch Testing							
Patch Test Material Placement		X			X		
Patch Test Material Removal							
Photographs							
Patch Test Site Photographs		X	X		X	X	
Dermatitis Photographs			X			X	X

\*In addition to the allergen patch site and normal skin, an additional biopsy will be done on an area of persistent dermatitis if present unless in an anatomic location not amenable to biopsy (face, hands, elbows, knees, genitals, feet).

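### Non-serious adverse event collection starts at the first dose, 72 to 120 hours after the baseline allergen challenge, and does not agree with the visit schedule

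*Combined protocol and SAP*

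**What the plan says.** All references are to the combined protocol and SAP.

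- **Start of collection.** Section 7.2.2: "Non-serious adverse event collection should begin at the time that dupilumab is first administered". For serious events Section 7.2.1 sets an earlier start: "Serious adverse event collection should begin at the time that informed consent is obtained".
- **Baseline challenge.** Inclusion criterion 2 (Section 4.2.1) gives its timing as "placement at Week 0 and patch test reaction read at Week 0 +72-120 hours".
- **First dose.** Section 5.3: "Two doses of dupilumab, 300 mg/2 mL, will be administered subcutaneously using the prefilled syringe at week 0 +72-120 hours". This is the same visit as the patch reading (Visit 3).
- **Schedule.** In Section 6.1 the row "Adverse Events" is blank at screening. It is marked at Week 0, Visit 3, Week 6, Week 12, Visit 6 and early termination. It makes no split between serious and non-serious events.
- **Scope.** Section 7.1: "Adverse events are not limited to those related to study drug".
- **Causality.** Section 7.1.3: "An adverse event may be related (reasonable causal relationship between dupilumab administration and the event) or not related". Section 7.2.1 also requires a serious event after the 30-day period to be reported if it "is related to dupilumab or procedures performed in the study".
- **Who is evaluated.** Section 6.3 evaluates safety in subjects who receive a dose. Under Section 4.1, subjects without a 2+ or 3+ reaction at Visit 3 are screen failures and are not dosed.

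**The concern.** In many trials the period before the first dose is passive screening, and starting non-serious collection at dosing loses little. Here that period contains a study procedure: deliberate re-exposure to an allergen that gave a strong or extreme reaction within the previous 18 months. Subjects enter with an IGA of at least 3 and have had no topical corticosteroid or calcineurin inhibitor for a week. A non-serious flare after placement is therefore plausible, and Section 7.1 puts it in scope as an adverse event.

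The challenge is repeated at Week 12. If the first one falls outside the collection window and the second inside it, the safety record of one procedure depends on when it was done. Staff who follow Section 7.2.2 and staff who follow Section 6.1 could also build different adverse event data for the same subject.

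**Working it through.** No sample size, power or rate enters this point. The check is a comparison of dates and rules.

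**Length of the interval.** The schedule puts Week 0 on Day 1 and Visit 3 on Day 4: 4 − 1 = 3 days, or 3 × 24 = 72 hours. The visit label allows up to 120 hours, or 120 / 24 = 5 days. At the end of the study, Day 87 − Day 84 = 3 days, again 72 hours nominal and up to 120 by the label. The two challenge intervals are the same length by design.

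**What is recorded as an adverse event under each rule.**

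| Event | Section 7.2.2 governs | Section 6.1 governs, mark covers all events |
|---|---|---|
| Non-serious, begins between Week 0 placement and first dose, subject later dosed | No | Yes (Visits 2 and 3) |
| The same, subject screen-fails at Visit 3 | No; collection never starts | Yes (Visits 2 and 3) |
| Non-serious, starts or worsens after first dose | Yes | Yes |
| Non-serious, after Week 12 placement | Yes | Yes (Visits 5 and 6) |
| Serious, any time from consent | Yes | Yes |

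The rules differ only in the first two rows.

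**Could the Week 0 mark mean serious events only?** That would remove the conflict of wording, since serious events are collected from consent. The schedule does not say so. Even on that reading the first two rows stay at No, so the gap remains.

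**What other records cover the interval?** The patch-site reaction is graded at Visits 3 and 6 and photographed at Visits 2, 3, 5 and 6, so the local reaction is documented alike at both challenges. Away from the patch site, dermatitis is photographed at Visits 3 and 6 but not at Week 0, and IGA, EASI and BSA are not scheduled at Visit 3. A photograph at Visit 3 alone cannot show a change since placement. Nor does it carry the onset, duration, intensity, causality and treatment that Section 7.2 asks for.

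**Causality.** Sections 7.1.3 and 7.2 ask for relation to dupilumab only. The late-reporting rule in Section 7.2.1 also needs a judgement about study procedures, which neither section tells staff to record. The adverse event form is not in the documents, so it may already hold such a field.

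**The case against.** The strongest reply is that the sections can be read together: the Week 0 mark serves serious events, and Section 7.2.2 fits Section 6.3, which evaluates safety in dosed subjects. That is a possible reading. It removes the contradiction but leaves the pre-dose events uncollected.

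Other parts of the reply stand and limit the point. A reader might infer any of the following, and the documents do not support them:

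- *Challenge harms are definitely counted at Week 12 and not at baseline.* This follows only if Section 7.2.2 governs or the Week 0 mark is confined to serious events.
- *The only within-subject comparator is lost.* The patch reaction is graded and photographed at both challenges. Vesicles are part of the 2+ and 3+ grades and irritant reactions have their own code (Section 2.1), so blistering at the site is recorded. Nothing says that the expected patch reaction becomes an adverse event at Week 12.
- *A planned analysis is biased.* Section 9.4.2 plans no comparison of adverse events before and after treatment.
- *Screen failures carry most of the hidden risk.* Those who fail at Visit 3 are the subjects who did not mount a 2+ or 3+ reaction.
- *Half of all challenges in treated subjects being outside the window measures the loss.* That counts challenges, not missed events.

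The lack of a procedure-relatedness field is a minor matter: a patch-related event can be classed as not related to dupilumab and placed by its onset date.

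**Conclusion.** The point holds in limited form. Section 7.2.2 states a start that comes 72 to 120 hours after the first study intervention, and Section 6.1 does not match it. If Section 7.2.2 governs, the loss is confined to non-serious events that begin in that interval and do not worsen after dosing, plus all non-serious events in challenged subjects who are never dosed. Any informal comparison of challenge-related events between Week 0 and Week 12 would then lean towards more events at Week 12.

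The size cannot be given, because the documents report no rate of such events; if few occur, the effect is small. The conclusion assumes that no operational document outside this protocol already sets an earlier start. It is a correction worth making to the safety record and does not threaten the trial's main result.

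**What to change.** 1. In Section 7.2.2, start non-serious collection at Week 0 patch placement, for every challenged subject, including those who screen-fail at Visit 3. This matches the mark in Section 6.1.
2. State that the Visit 3 adverse event review is done before dosing, so that events can be dated as before or after the first dose.
3. In Section 9.4.2, tabulate events before the first dose separately from treatment-emergent events, so that the wider window does not inflate the latter. List events in challenged but undosed subjects separately, since Section 6.3 leaves them out.
4. Optionally, add relation to study procedure to the adverse event record (Sections 7.1.3 and 7.2), because late reporting under Section 7.2.1 depends on it.

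The reviews at Week 0 and Visit 3 are already scheduled, so the cost is protocol wording and, for item 4, perhaps one form field. The downside is a few more mild events to record.
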